Participants randomized to the Patient Choice between facilitated DOT and facilitated SAT arm will be offered a choice between arms 1 and 2. A research nurse will review each section of the decision aid with participants, discuss values and preferences, and, after addressing any questions, ask participants to select facilitated DOT or facilitated SAT. Participants will have the option to switch between DOT and SAT at any time. The reason for switching and time spent under each strategy will be recorded.

Eligibility Criteria

To be included in the randomized trial, patients will have to meet all of the following inclusion criteria and none of the exclusion criteria:

1. Inclusion Criteria:

- a. HIV-positive client engaged in care at the Mulago ISS clinic
- b. Weight $\geq 40\text{kg}$
- c. Age 18 years or older
- d. Capacity to provide informed consent in English or Luganda

(From our experience conducting similar studies at the Mulago ISS clinic, the majority of patients receiving care at the clinic are able to communicate using the Luganda language. For example, while

conducting patient Knowledge, Attitudes and Practices (KAP) interviews during the formative phase, 21/25 (84%) participants opted for Luganda and only four of the 25 opted for English as the language for the interview. Therefore, in addition to Luganda, we selected English as the other preferred language for the study)

2. **Exclusion Criteria:**

- a. Suspicion of active TB based on positive WHO symptom screen AND elevated POC CRP, or current or planned TB treatment
- b. Actively taking an antiretroviral medication contraindicated for use with rifapentine under contemporary WHO or Ugandan policy
- c. Contact of a TB patient with known resistance to isoniazid or rifamycins
- d. Women who are pregnant, breast feeding or intending to get pregnant in the next 120 days. Note: women who become pregnant while on 3HP will be recommended to continue and complete 3HP treatment per Uganda 2020 Uganda National Guidelines, and will be monitored for side effects as per the study protocol ²⁶
- e. Prisoners
- f. Previously completed treatment for active TB or at least 6 months of isoniazid preventive therapy within past 2 years
- g. Not intending to remain within 25 km of the Mulago ISS clinic during the study period or to receive further care at the Mulago ISS clinic
- h. Lack of access to a mobile telephone or lack of willingness to receive SMS reminders/IVR phone calls

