- i. Pre-existing documentation of clinical liver disease.
- j. History of sensitivity or intolerance to isoniazid or rifamycins
- k. Another household member already enrolled in the study (household members cannot be effectively randomized to different arms)
- l. Actively taking medication contraindicated for use with rifamycin (e.g., warfarin, phenytoin)

Mixed methods and health economic sub-studies will include a subset of participants enrolled in the trial, as well as clinic administrators and clinicians (clinical officer, doctor, nurse, pharmacist, peer educators and counselors) involved in 3HP delivery at the Mulago ISS clinic.

Recruitment and eligibility screening

PLHIV will be recruited through Mulago ISS clinic providers, who will refer interested clients to study staff for eligibility screening, or directly from the patient waiting area by a trained research nurse. In order to be considered for study entry, all interested clients must have completed the following screening evaluations/documentation:

- A baseline medical history and clinical evaluation, including:
 1. Patient demographics (i.e., sex, age)
 2. Access to mobile telephone/willingness to receive SMS reminders/IVR phone calls
 3. Intention to remain within 25 km of the Mulago ISS clinic during the study period or to receive further care at the Mulago ISS clinic
 4. Height and weight
 5. Previous treatment for LTBI (i.e., if patient has previously completed a full course of 3HP or at least 6 months of isoniazid preventive therapy)
- Evaluation of contraindications for 3HP treatment, including:

1. Active treatment with an antiretroviral medication contraindicated for use with rifapentine under contemporary Ugandan policy
2. Current breastfeeding, pregnancy, or a plan to get pregnant within 120 days of enrollment (a pregnancy test in women of childbearing potential must be obtained \leq 14 days prior to enrollment).
Note: women who become pregnant while on 3HP will be recommended to continue and complete 3HP treatment per Uganda 2020 National Guidelines, and will be monitored for side effects as per the study protocol.
3. Contact of a case with known resistance to INH or rifapentine.
4. Risk for underlying liver disease which includes pre-existing documentation of clinical liver disease.

- Laboratory tests, including:
 1. A blood or urine pregnancy test done on all women of reproductive potential.
- Evaluation for active TB

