 1. Symptom screen and if positive POC CRP measurement via finger prick blood sample

Clients who do not meet the eligibility criteria at the time of screening may be eligible at a later time. Therefore, clients can be subsequently re-screened (i.e., screened more than once) in order to be eligible for the study.

Written Informed consent

A research nurse will read aloud from an institutional review board (**IRB**)-approved consent form in the client's preferred language (English or Luganda). A copy of the consent form in the client's preferred language will also be given to the client. If the client is illiterate, a third party of the client's choice will be asked to witness the consent. While participants will be encouraged to ask additional questions throughout the consent process, at a minimum the following areas will be addressed.

- Participant rights
- Purpose
- Procedures
- Risks and side effects
- Benefits
- Alternatives
- Questions

At the conclusion of discussions of these topics, the eligible participant will be asked, "Do you wish to participate?" after making it clear that a decision to consent or not will not affect the client or any of his or her family members' right to receive standard prevention, care, and treatment for TB or HIV. If the client agrees, he or she will be asked to sign his or her name on the consent form, or, if illiterate, to provide witnessed consent by someone who is not part of the research team, as described above. In all cases, the nurse will also sign his/her name as a witness. The consent forms, which will be approved by IRBs in the U.S. and Uganda, will be translated from English into Luganda, and back-translated into English as required by IRBs to be sure that no significant language or concepts are lost in translation. If the client does not wish to participate, the nurse will thank the patient. Clients who are unable to communicate (because of altered mental status or inability to speak English or Luganda) may be excluded because of a lack of ability to provide informed consent.

Verbal Informed consent to participate in qualitative telephone interviews

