4. **Patient Costing:** To estimate any additional patient-level and societal costs of 3HP (e.g., ancillary healthcare visits, patient and caregiver costs associated with 3HP, use of formal social support programs), the time-and-motion studies will be supplemented by a patient costing survey (N=150, or 50 participants per arm).

Post-3HP treatment

All participants will be aggressively traced and asked to return to clinic (reimbursed in the usual fashion) after completion of their final medication dose, or at 16 weeks post-treatment initiation (for participants not completing treatment).

The following *routine TB preventive care activities* will be performed by Mulago ISS clinic staff during a routine HIV/AIDS care clinic visit:

Follow-up assessment: Participants will be screened for active TB for a period of two years after 3HP treatment completion (*i.e.*, up to 28 months after enrollment) at clinic visits for routine HIV/AIDS care. TB screening will include symptom assessment using the WHO four-symptom TB screen administered at every visit. For patients with new or progressive TB symptoms a chest X-ray (**CXR**) and sputum for Xpert MTB/RIF and mycobacterial culture will be performed, as per routine WHO and NTLP recommended procedures. Sputum will be induced, if needed. All participants diagnosed with TB at any time point will have sputum submitted for culture and drug susceptibility testing on liquid media. Loss to follow-up will be defined as a participant not able to be contacted and does not return to clinic within the 12-month post treatment follow-up period. At 28 months only, all clients who have not already been diagnosed with TB at any point during follow-up and regardless of any symptoms of TB will be asked to return to the clinic and submit sputum for Xpert MTB/RIF and mycobacterial culture for those with RIF resistance detected via Xpert MTB/RIF.

The following *study-specific activities* will be performed by research staff after 3HP treatment is complete:

1. **Survey 3:** Research staff will administer a survey to document the reason for treatment discontinuation (completed therapy, adverse event/intolerance, other) and to assess satisfaction with TB preventive care received. Study staff will use patient telephone numbers and addresses to contact study participants. If returning to clinic is not possible, the survey may be conducted over the phone.

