^a 3HP treatment may last up to 16 weeks^b Patients randomized to choice arm only^c Time-and-motion studies will be performed on 40 randomly selected days (one day per week throughout the year, stratified by day of week). We anticipate that this will capture up to 250 unique participant visits per arm (750 total).^d Patient costing surveys will include 50 participants from each arm, or 150 participants total^e Only if symptomatic, except at end of follow-up.^f 24 participants/arm

Outcome Measures

Primary Outcome (Effectiveness of delivery options)

Outcome	Numerator	Denominator
Proportion accepting and completing 3HP treatment	Number who take at least 11 of 12 doses within 16 weeks of treatment initiation	Number randomized

Secondary Outcomes (Quantitative)

Outcome	Numerator	Denominator
REACH		
Treatment acceptance	Number taking at least one dose of 3HP	Number randomized
EFFECTIVENESS		
Treatment completion	Number who take at least 11 of 12 doses within 16 weeks of treatment initiation	Number taking at least one dose of 3HP

Cost-effectiveness (overall)	(Cost in Arm A – cost in Arm B) from societal perspective	(DALYs averted in Arm A – DALYs averted in Arm B) from societal perspective
Cost-effectiveness (health system)	As above, but from health system/provider perspective	As above, but from health system/provider perspective
Cost-effectiveness (patient)	As above, but from patient perspective	As above, but from patient perspective
Safety	Number for whom treatment discontinued due to adverse events or intolerance.	Number taking at least one dose of 3HP
Cumulative incidence of TB at 16 months	Number diagnosed with TB during 16-month follow-up	Risk set*
Cumulative incidence of TB at 28 months	Number diagnosed with TB during 28-month follow-up	Risk set*
ADOPTION		
All Participants		
Visit Cost Reimbursement	Number of visits for which reimbursement provided on same day	Total number of DOT/refill visits
Time to complete clinic visit	Mean and median number of minutes for each DOT/refill visit	--
SMS or IVR phone call reminders delivered	Number of SMS or IVR phone call dosing or clinic visit reminders delivered	Total number of SMS reminders scheduled to be sent
SMS or IVR phone call reminders following missed appointments	Number of SMS or IVR phone call dosing or clinic missed appointment reminders delivered	Number of participant weeks with 3HP missed appointments
Screening for active TB	Number screened for active TB during DOT visits	Total number of DOT visits

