Screening for side effects	Number screened for side effects during DOT visits	Total number of DOT visits
Participants taking 3HP by SAT only		
Dosing confirmation via 99DOTS	Number of doses recorded by 99DOTS	Total number of scheduled doses (not including doses taken during clinic visits).
SMS or IVR phone call missed dose reminders delivered	Number of SMS or IVR phone call missed dose reminders delivered	Number of participant weeks with 3HP dosing not recorded by 99DOTS
SMS or IVR phone call weekly check-in delivered	Number of weekly SMS or IVR phone call check-ins delivered	Number of participant weeks taking 3HP (not including weeks where dosing is directly observed)

Follow up (phone calls or home visits) for negative response to weekly SMS or IVR phone call check-in	Number of follow-up calls and/or home visits completed following negative response to weekly SMS or IVR phone call check-in message	Number of participant weeks of negative response to weekly SMS or IVR phone call check-in messages
IMPLEMENTATION		
Costs of preventive services	Mean total patient costs related to TB preventive care services	
Participant satisfaction	Mean score on PSQ questionnaire	--
Barriers to 3HP delivery	Thematic interpretation of provider- and clinic-level barriers to care from provider focus group discussions	
Barriers to 3HP completion	Thematic interpretation of barriers to 3HP completion from patient interviews	

* Participants will be censored at the time of active TB diagnosis or treatment initiation, death, loss to follow-up (*i.e.*, unable to be contacted and have sputum collected between 10 and 28 months after 3HP treatment discontinuation or completion), or end of the 28-month post-treatment follow-up period

Statistical Considerations

1. Primary hypotheses:

- a. The proportion who accept and complete 3HP will be highest among PLHIV randomized to the informed choice arm.
- b. The proportion of PLHIV who accept and complete 3HP can exceed 80% in a high HIV/TB burden setting.

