### 3.7 Analysis of secondary outcomes

Secondary outcome analysis will include:

1. **Reach outcome(s):** 1) Unadjusted comparisons across arms, and 2) simple calculation of the proportion of patients randomized who accept treatment in each arm.
2. **Effectiveness outcomes:** 1) Occurrence of AEs across arms will be assessed using Chi-square tests and logistic regression; 2) Incidence of active TB will be assessed using Kaplan-Meier curves, log-rank tests, and Cox proportional hazards methods as appropriate. Assessment for active TB occurs at 15-16 months post enrolment. Survival analyses will include:
  - o An assessment of the incidence rate of TB, comparing across arms (DOT vs. SAT vs. Choice) using Kaplan Meier, time-to-event analyses. We will estimate the difference in the Kaplan Meier and Cox proportional hazard estimators for the survivor functions, comparing the arms to get hazard ratios and 95% CIs.
  - o An assessment of the incidence rate per arm by drug compliance, which will include for each arm: a comparison of the incidence of active TB in those within the arm that complete at least 11 of the 12 doses within the allotted 16 weeks vs. the incidence of active TB in those within the arm that complete  $\leq$ 10 doses of 3HP. We will estimate the difference in the Kaplan Meier and Cox proportional hazard estimators for the survivor functions, comparing the arms to get hazard ratios and 95% CIs.

3. **Adoption outcomes:** For each process metric, we will report the monthly proportion (and 95% CI) number, or median (interquartile range (IQR)) to assess the implementation of intervention components in each arm.
4. **Implementation outcomes:** Quantitative data will be assessed using multivariable regression models to compare by study arm patient survey data including a) patient costs; b) scores on questions related to patient barriers to TB preventative care; and c) patient satisfaction. Qualitative data will be analysed using appropriate software where open coding will be applied to generate codes and themes. Thematic groupings will be developed and reviewed to identify emergent themes within each domain of the coding framework and quotes that best represent each domain. Thematic interpretation will include collaborative development of a coding framework and detailed coding of transcripts.

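### TB already present at enrolment can be reported as incident TB, because entry screening includes no sputum test and neither document has a rule for early diagnoses

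*Protocol*

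**What the plan says.** **Entry.** Exclusion criterion (a) in the protocol's Eligibility Criteria removes clients with "Suspicion of active TB based on positive WHO symptom screen AND elevated POC CRP, or current or planned TB treatment". The TB work-up under Recruitment and eligibility screening is "Symptom screen and if positive POC CRP measurement via finger prick blood sample". The only item listed there as a laboratory test is "A blood or urine pregnancy test done on all women of reproductive potential". Neither sputum nor a chest X-ray is listed at entry.

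**Outcome.** The Outcome Measures table gives the two TB numerators as "Number diagnosed with TB during 16-month follow-up" and "Number diagnosed with TB during 28-month follow-up", each over a risk set. The footnote on that risk set says "Participants will be censored at the time of active TB diagnosis or treatment initiation, death, loss to follow-up" or at the end of follow-up. Objectives 5 and 6 in section III sort cases into definite and probable by how TB was confirmed, not by when it began.

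**Analysis.** SAP 3.7, item 2, plans "An assessment of the incidence rate of TB, comparing across arms (DOT vs. SAT vs. Choice) using Kaplan Meier, time-to-event analyses", with log-rank tests and Cox hazard ratios. It then compares TB within each arm between participants who took at least 11 doses in 16 weeks and those who took 10 or fewer. No text in either document sets a window, landmark or sensitivity analysis for early diagnoses. SAP 2.3 says the SAP takes precedence, and it is silent here.

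**Follow-up.** Clinic staff screen for TB symptoms at each DOT or refill visit: weekly under DOT, weeks 6 and 12 under SAT. Sputum regardless of symptoms is collected only at month 28.

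**Time origin.** The Post-3HP treatment section follows participants "up to 28 months after enrollment", and SAP 3.7 also times the TB assessment from enrolment. The risk-set footnote instead ends follow-up 28 months after treatment.

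**The concern.** Objectives 5 and 6 ask for the incidence of active TB, which means new disease. Two groups can enter with TB that the screen has not found: clients without symptoms, who have no further test, and clients with symptoms whose CRP is not elevated. If such a person is diagnosed during follow-up, the outcome table counts an incident case after 3HP was offered, although the disease came before the first dose.

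Three things are at stake:

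- Each arm's cumulative incidence reads too high.
- Disease present before randomization cannot depend on the delivery strategy, so it adds about equally to every arm and moves the hazard ratios towards 1.
- The within-arm comparison by completion is affected in the opposite direction. The protocol leaves it to clinicians whether 3HP continues when TB is suspected. TB found early can therefore end treatment and place the person in the group with 10 or fewer doses.

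**Working it through.** The documents state no TB prevalence, incidence or power, so there is no figure of theirs to reproduce. Every prevalence and rate below is an assumption.

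**1. Inflation at 16 months.** True risk = 1 − exp(−rate × 16/12). The upper limit of the reported risk is true risk + undetected prevalence. It is an upper limit because it supposes that every prevalent case is diagnosed by month 16.

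- Rate 1 per 100 person-years: 1 − exp(−0.0133) = 1.32%. With prevalence 0.5%, at most 1.32 + 0.50 = 1.82%. The prevalent share of counted cases is at most 0.50/1.82 = 27%.
- Same rate, prevalence 1%: relative inflation at most 1/1.32 = 76%.
- Rate 3 per 100 person-years: 1 − exp(−0.04) = 3.92%. With prevalence 0.25%, inflation is at most 0.25/3.92 = 6%.

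**2. Dilution between arms.** Observed risk = prevalence + (1 − prevalence) × true risk, with equal prevalence and equal detection in the arms. Take a true risk of 2% in the reference arm and a true ratio of 0.50. The risk ratio stands in for the hazard ratio, which is reasonable at low risk. Power is for 552 per arm at two-sided 0.05.

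| Prevalence | Risks | Ratio | Difference (points) | Power |
|---|---|---|---|---|
| 0 | 2.00% vs 1.00% | 0.50 | 1.00 | 0.28 |
| 0.5% | 2.49% vs 1.50% | 0.60 | 0.995 | 0.22 |
| 1% | 2.98% vs 1.99% | 0.67 | 0.99 | 0.18 |
| 2% | 3.96% vs 2.98% | 0.75 | 0.98 | 0.14 |

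The ratio moves and the absolute difference hardly does.

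**3. A contrast nearer the trial's own.** Take completion of 80% versus 90% (a row of Table 3), a 50% reduction in TB (top of the protocol's 30–50% Background range) and an assumed untreated risk of 4%. The risks are 0.04 × (1 − 0.5 × 0.8) = 2.4% and 0.04 × (1 − 0.5 × 0.9) = 2.2%, a ratio of 0.917. At 1% prevalence they become 3.38% and 3.18%, a ratio of 0.941. Power to find the difference in the expected direction is about 4% either way.

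**4. Comparison by completion.** An extreme case shows the direction. In one arm, 0.5% × 552 = 2.8 people have TB at entry. At 80% completion there are 0.2 × 552 = 110 non-completers. If all 2.8 are found during treatment and stop 3HP, they add 2.8/110 = 2.5 points to the non-completers' TB risk and nothing to the completers'. Completers must also stay on treatment long enough for 11 weekly doses, which is at least 10 weeks from the first.

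**5. What a 16-week cut would set aside.** True new TB in 16 weeks is 1 − exp(−0.01 × 16/52) = 0.31% at 1 per 100 person-years and 0.92% at 3 per 100. Suppose every prevalent case surfaces by week 16 and new cases are diagnosed promptly. The truly new share of the early cases is then 0.31/(0.31 + 0.50) = 38% at 0.5% prevalence and the lower rate. At 0.25% prevalence and the higher rate it is 0.92/(0.92 + 0.25) = 79%. If fewer prevalent cases surface by then, these shares rise. In person-time, 16 weeks is 3.7 months: 23% of 16 months and 13% of 28.

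**The case against.** This is a pragmatic trial, and TB diagnosed after randomization in people who passed its screen is a legitimate outcome. Counting from randomization keeps the arms comparable. That stands, and it is why the from-enrolment analysis should remain the main one. It does not make the result an incidence of new disease, which is what the objectives ask for.

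A reader might take 6% to 76% as the expected inflation. The documents do not support that. Both inputs are assumed, and testing depends on symptoms until month 28, so TB without symptoms may not surface by month 16. The figures are upper limits within each scenario.

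A reader might also infer that a 16-week TB-free landmark should replace the main analysis. It should not. DOT participants are screened weekly and SAT participants at weeks 6 and 12, so being TB-free at week 16 is a post-randomization condition that can differ by arm. The landmark would drop many truly new cases (step 5) and would keep prevalent cases found later.

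Finally, the protocol footnote can be read as starting the clock after treatment, which would leave on-treatment diagnoses out already. The Post-3HP treatment section and SAP 3.7 both point to enrolment, so that reading is the weaker one, but the conflict is real.

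**Conclusion.** The gap is real and its consequence modest. As written, the plan will report some TB present at entry as incident. Each arm's cumulative incidence rises by at most the undetected prevalence, and between-arm hazard ratios move towards 1. The dilution assumes that randomization balances prevalence and that detection is similar across arms; the different screening schedules could disturb the second assumption in either direction. The size cannot be fixed from the documents.

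It would go too far to say that every TB comparison is biased towards no difference: absolute differences are nearly unchanged, and the completion comparison is exaggerated. It would also go too far to say that the trial's main conclusion is at risk. Both primary hypotheses concern acceptance and completion, TB is a secondary outcome, and power for it is low with or without prevalent cases.

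**What to change.** In SAP 3.7 and the protocol's outcome table:

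- Keep the analysis of all randomized participants from enrolment as the main one, and label it as all TB diagnosed after enrolment.
- Report TB diagnosed in the first 16 weeks separately by arm, as possible prevalent or on-treatment TB.
- Pre-specify a sensitivity analysis of incidence and hazard ratios starting 16 weeks after enrolment, among participants alive and TB-free then.
- Use the 16-week landmark for the comparison by completion. The SAP counts completion from treatment initiation, so state how participants whose first dose came after enrolment are handled.
- Reconcile the end of follow-up: 28 months from enrolment in one section, 28 months after treatment in the risk-set footnote. SAP 2.1 and 3.7 should also cover the 28-month outcome, which they omit.

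The cost is some wording and one extra analysis on dates already collected, with no change to screening or care. The landmark version loses early person-time and true early cases, conditions on post-randomization status under unequal screening, and still contains prevalent cases found after week 16. It supports the main analysis and does not replace it.
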